8.6 Study Variables

Type	Variable	Conceptual Definition	Operational Definition	Indicator (unity)	Scale
Independent	Cocoa supplementation	Cocoa powder capsules	4 cocoa powder capsules providing 50 mg of flavonoids (12.5 mg per capsule), administering two capsules in the morning and two capsules at night, every day, for three months. (Appendix 2)	Present (supplement) / Absent (placebo)	Qualitative nominal dichotomous
Dependent	Peripheral diabetic neuropathy	Presence of signs and/or symptoms of peripheral nerve dysfunction in people with diabetes, after excluding other causes. (50)	
It is obtained after applying the MNSI questionnaire regarding symptoms (filled out by the patient and with a maximum score of 13 points) and the physical examination (evaluated by the researcher) with a maximum score of 13 points. (Appendix 3) (51)
 
Toronto Clinical Scoring System: is a clinical evaluation system carried out by the researcher, assigning a score to the symptoms, reflexes and sensory tests. (33, 34) (Appendix 4)
 
H reflex test: This is performed by electrical stimulation, placing the active electrode on the Achilles tendon, the positive electrode above the gastrocnemius and the reference electrode at the height of the gastrocnemius heads. Stimulation is carried out behind the knee (anatomical site of the tibial nerve). The electrical stimulus consists of the application of 10 pulses (1 every 10 seconds) and the maximum intensity applied is according to the sensitivity and tolerance of each individual. (18, 36)
	
Total sum of points obtained from the application of the MNSI questionnaire No unit
 
6-8 points: mild DN 9-11 points: moderate DN 12-19 points: severe DN
 
Total sum of points obtained from the application of the TCSS No unit
 
Quotient R2/R1 μV
	Discrete quantitative Qualitative ordinal Discrete quantitative Discrete quantitative

Dependent	Autonomic diabetic neuropathy	Damage to the nerves that control internal organs, causing alterations in various systems such as the cardiovascular, gastrointestinal and urogenital systems. (20)	
- BEST questionnaire: Includes: 1) severity of intestinal symptoms; 2) impact of symptoms on the ability to enjoy everyday things; 3) patient perception of the condition; and 4) impact of symptoms on mood and humor. Scale from 0 to 100 according to the subject's responses. (Appendix 5) (52)
 
-Bristol scale: It is made up of 6 categories that include an image and an explanation, ranging from 1 to 7, with 1 being hard, separated pieces that pass with difficulty and 7 being watery stools. (Appendix 6) (53)
	No unit	Continuous quantitative
				No unit	Discrete quantitative
Dependent	Weight	Total body mass of an individual (54)	Weight of an individual in kg determined by the scale. The measurement is carried out without shoes and with the minimum possible clothing. The subject must be placed in the center and remain motionless during the measurement. (54)	kg	Continuous quantitative
Dependent	Waist circumference	Body measurement used as an indicator of central adiposity, as well as cardiovascular risk (55)	The tape is placed in a horizontal plane around the waist, taking the midaxillary line as a reference, locating the midpoint between the lower costal margin and the highest lateral edge of the iliac crest. (55)	cm	Continuous quantitative
Dependent	Waist-to-height ratio (WtH)	Index resulting from dividing the waist circumference by the height. (74)	It is obtained by dividing the waist circumference in cm by the height in cm, with a result of ≥ 0.5 indicating an increased risk for cardiometabolic disease. (74)	No unit	Continuous quantitative
Dependent	Abdominal circumference	Body measurement that directly correlates with visceral fat. (54)	The top of the hip bone and the top of the right iliac crest are located and the tape measure is placed horizontally around the abdomen, at the level of the iliac crest, at the end of a normal expiration. (55)	cm	Continuous quantitative

Dependent	Arterial Pressure	Hydrostatic force of blood on arterial walls resulting from the pumping function of the heart, blood volume, resistance of the arteries to flow, and diameter of the arterial bed. (56)	A sphygmomanometer is used to obtain blood pressure using the technique specified in the Clinical Practice Guidelines for the diagnosis and treatment of arterial hypertension in the primary care level. (57)	mmHg	Continuous quantitative
Dependent	Neutrophil/lymphocyte ratio	Index resulting from the division of the serum concentration of neutrophils by the serum concentration of lymphocytes. (75)	It is obtained by dividing the serum concentration of the absolute number of neutrophils by the serum concentration of the absolute number of lymphocytes. (75)	No unit	Continuous quantitative
Dependent	Glycemia	Blood glucose concentration (58)	Obtained from laboratory study by spectrophotometry of blood sample, with a fasting period of 8 hours. (59)	mg/dL	Continuous quantitative
Dependent	Glycated hemoglobin (HbA1c)	Value of the fraction of hemoglobin that has glucose attached (58)	Analyzed by high-performance liquid chromatography (HPLC), without a specific fasting period for this test. (62)	%	Continuous quantitative
Dependent	Triglyceridemia	Blood triglyceride concentration (58)	Obtained from a laboratory study by spectrophotometry of the lipid profile of a blood sample, with a 12-hour fasting period. (59)	mg/dL	Continuous quantitative
Dependent	High density cholesterol (HDL-c)	HDL-c concentration in blood.	Obtained from a laboratory study by spectrophotometry of the lipid profile of a blood sample, with a 12-hour fasting period. (59)	mg/dL	Continuous quantitative
Dependent	Low density cholesterol (LDL-c)	LDL-c concentration in blood.	Obtained from a laboratory study using spectrophotometry of the lipid profile of a blood sample, with a fasting period of 12 hours. (59)	mg/dL	Continuous quantitative
Dependent	Triglycerides/HDL-c ratio (TG/HDL)	Index resulting from the division of the serum concentration of triglycerides by the serum concentration of HDL (63)	It is performed after dividing the serum triglyceride concentration in mg/dL by the serum HDL concentration in mg/dL.(63)	No unit	Continuous quantitative
Dependent	Diabetes 39 questionnaire	Questionnaire designed to measure quality of life in patients with type 1 and type 2 diabetes. (64)	Questionnaire containing 39 closed items grouped into 5 sections: energy and mobility, diabetes control, anxiety-worry, social burden and sexual functioning. Subjects rate their perception of their quality of life	No unit	Discrete quantitative

			in a global manner, with a range from 1 (minimal) to 7 (extremely severe), and the scores obtained are transformed into a scale of 0 to 100. (Appendix 7) (64)		
Confounding	Hypoglycemic drugs	Drugs that lower or regulate glucose. (65)	The use of hypoglycemic drugs will be considered when the patient is taking any drug from the following groups: Sulfonylureas (glibenclamide), biguanides (metformin), glinides, thiazolidinediones or glitazones, GLP-1 analogues, DPP4 inhibitors (sitagliptin) and alpha glucosidase inhibitors (acarbose). (66)	Present/ Absent	Qualitative nominal dichotomous

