There is no standard for the evaluation of ADN, however, the clinical history is essential, for example, for the evaluation of gastrointestinal ADN, tests that identify symptoms such as nausea, vomiting, abdominal pain, constipation or diarrhea can be used (35), such as the Bristol scale and the BEST questionnaire.

2.6 *RDD of the H-reflex*

The Hoffman reflex (H-reflex hereafter) is produced by an electrical pulse and is recorded in a given muscle, and is analogous to the muscle spindle stretch reflex generated by a mechanical stimulus (myotatic reflex). The H-reflex represents the excitability of the alpha motor neuron (α MN) when presynaptic inhibition and the intrinsic excitability of α MNs remain constant. This test allows the evaluation of the response of the nervous system in conditions of damage to the nerve fibers and the somatosensory processing in the spinal cord. (36) Through the H-reflex, it is possible to measure the efficacy of synaptic transmission of afferent fibers (Ia sensory) to α MNs. The evoked afferent response starts at the point of electrical stimulation, resulting in action potentials that travel along the afferent fibers until they synapse in the α MNs, while on the efferent side, the action potentials travel along the fibers until they reach the neuromuscular junction and produce a contraction response that can be recorded in the electromyogram. (36)

An additional test based on the H reflex is the rate-dependent depression (RDD) test, which is a measure of the change in the amplitude of the spinal H reflex during consecutive paired electrical stimulations at different frequencies (<1 Hz). Recently, it has been described that RDD is affected after disinhibition of spinal sensory processing, e.g., in animal models of experimental diabetic neuropathy (18, 37, 38) and in T1D in humans (18), so the paired-pulse H reflex allows the objective and noninvasive detection of alterations in nerves and spinal sensory processing.

2.7 *Treatment*

Up to 50% of DN can be asymptomatic, and if not recognized and treated in time, it increases the risk of injuries, decreased quality of life, and even mortality, as in the case of cardiovascular ADN. Currently, the management of DN consists of lifestyle modifications to control glycemia

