8.8 STATISTICAL ANALYSIS

A descriptive analysis of all dependent variables, as well as demographic variables, will be performed, expressing them as mean \pm standard deviation or, where appropriate, as median and range (min-max), according to the normality of the data; nominal variables will be expressed as frequencies. Subsequently, an intragroup inferential analysis will be carried out for weight, waist circumference, abdominal circumference and blood pressure with ANOVA for repeated samples with Tukey *post hoc*, and in case the data distribution does not meet the normality criteria, the corresponding nonparametric test will be performed (e.g.,

Friedman, followed by Dunn's *post hoc*). For biochemical analysis (glycemic and lipid profile and markers of inflammation), as well as the evaluations corresponding to diabetic peripheral and autonomic neuropathy, and quality of life, a Student's T test will be performed for dependent groups, or where appropriate, with Wilcoxon.

The intergroup comparison will be made with Student's T test for independent samples, or if applicable, with Mann-Whitney U at each measurement time. A $p < 0.05$ will be considered as statistical significance. All of the above will be carried out using version 5 of the GraphPad Prism software.

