Appendix 6: Bristol Scale

Tipo 1		• Tipo 1: Trozos duros separados, como nueces, que pasan con dificultad.
Tipo 2		• Tipo 2: Como una salchicha compuesta de fragmentos.
Tipo 3		• Tipo 3: Con forma de morcilla con grietas en la superficie.
Tipo 4		• Tipo 4: Como una salchicha; o serpiente, lisa y blanda.
Tipo 5		• Tipo 5: Trozos de masa pastosa con bordes definidos, que son defecados fácilmente.
Tipo 6		• Tipo 6: Fragmentos blandos y esponjosos con bordes irregulares y consistencia pastosa.
Tipo 7		• Tipo 7: Acuosa, sin pedazos sólidos, totalmente líquida.

Traducido de: Heaton, KW, Lewis, SJ. Stool form scale as a useful guide to intestinal transit time.
Scandinavian Journal of Gastroenterology 1997 (32): 9, 920-4

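### The Bristol scale is tested as a raw 1–7 number although both ends are symptomatic, so a real benefit can read as no effect and a raw shift has no direction

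*Combined protocol and SAP*

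**What the plan says.** Section 8.6 lists two measures under autonomic diabetic neuropathy: the BEST questionnaire and the Bristol scale. The Bristol entry is scored from 1 to 7, "with 1 being hard, separated pieces that pass with difficulty and 7 being watery stools", and its measurement level is given as "Discrete quantitative". Appendix 6 shows the two ends as opposites: "Tipo 1: Trozos duros separados, como nueces, que pasan con dificultad" and "Tipo 7: Acuosa, sin pedazos sólidos, totalmente líquida".

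Section 2.5 explains why these tools were chosen. For gastrointestinal autonomic neuropathy, "tests that identify symptoms such as nausea, vomiting, abdominal pain, constipation or diarrhea can be used", with the Bristol scale and BEST given as examples. Effect on gastrointestinal symptoms is one of the nine specific objectives in section 7.1.

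Section 8.7 has the scale applied at the start and at the end of the study. Section 8.8 puts the "evaluations corresponding to diabetic peripheral and autonomic neuropathy, and quality of life" through a paired t-test or Wilcoxon test within each arm. Between arms it uses an independent t-test or Mann-Whitney test at each measurement time.

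No section names a normal stool type or band, says which direction counts as improvement, recodes the score, or separates patients by baseline stool pattern. The selection criteria in section 8.5 do not restrict entry to one pattern.

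**The concern.** The planned tests assume that a higher number means more, or less, of something that matters to the patient. The Bristol scale does not work that way, because by the protocol's own account trouble lies at both ends. Two consequences follow.

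- **Offsetting.** If cocoa helps constipated and loose-stool patients alike, their changes carry opposite signs. The arm mean, or the rank sum, may hardly move.
- **No direction.** A significant rise in the raw score could be relief of constipation or new loose stools. The test cannot tell them apart. Rank tests do not help, because ranks follow the same raw order.

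At stake is the usefulness of one of the two autonomic measures, in a trial whose title names autonomic neuropathy.

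**Working it through.** **1. The plan's own figure.** No calculation is given for the Bristol scale. Section 8.4 sizes the trial on the TCSS: 2 × (1.96 + 0.84)² × 0.84² / 0.776² = 15.68 × 0.7056 / 0.6021 ≈ 18.4, stated as 18 per group. (The printed formula squares only the second Z value, but the 15.68 shows that the sum was squared.) I use 18 per arm and two-sided 0.05.

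**2. Sign check.** With type 4 taken as the centre for illustration:
- 2 → 4 scores +2 and 6 → 4 scores −2. Both improve, and the sum is 0.
- 1 → 4 scores +3 and 4 → 7 scores +3. One is relief and the other is harm, but the score is the same.

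The second line holds for any mix of patients.

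**3. Expected arm difference.** Let c and l be the shares constipated (types 1–2) and loose (types 6–7), r the response rate, and two types the size of the move. Ignoring noise:
- raw score: 2r(c − l)
- distance from type 4: −2r(c + l)

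With r = 0.75 and c = l = 0.40, the raw difference is 2 × 0.75 × 0 = 0 and the distance difference is −2 × 0.75 × 0.80 = −1.20. Simulation with month-3 noise gives −0.01 and −1.06. Noise shrinks the distance effect because it pushes some patients off the centre again. With c = 0.60 and l = 0, the raw difference is 0.90 and nothing cancels.

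**4. Power by simulation.** Assumptions that are not in the documents: remaining patients at types 3–5; 75% of abnormal cocoa patients move two types toward type 4; no change on placebo; a random ±1 step in 30% of patients at month 3. Monte Carlo error is about one percentage point.

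| Constipated / loose | Raw score, t-test | Distance from 4, t-test | Distance, adjusted for baseline distance |
|---|---|---|---|
| 40% / 40% | 6% | 91% | 99% |
| 30% / 30% | 6% | 68% | 88% |
| 50% / 10% | 21% | 68% | 87% |
| 60% / 0% | 48% | 66% | 87% |
| 15% / 15% | 5% | 26% | 37% |

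The last column is probably optimistic, since the model puts no measurement noise on the baseline score.

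**5. Dependence on the mix.** With 70% of patients abnormal and 80% responding, raw-score power (t-test / Mann-Whitney) by constipated/loose share is:
- 35/35: 6% / 7%
- 45/25: 9% / 12%
- 52.5/17.5: 17% / 24%
- 60/10: 34% / 44%
- 70/0: 69% / 72%

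Mann-Whitney power on distance stays at 84–86% throughout. With no effect, all tests reject in about 5% of trials.

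**6. Weaker inputs.** Distance from type 4 (unadjusted t-test) also has low power when few patients are abnormal or the response is small: 15% at 10/10, 26% at 40/40 with a 30% response, and 24% at 30/30 with a one-type move.

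**The case against.** The strongest reply is that cancellation needs a fairly even split of constipated and loose-stool patients, and nothing in the documents says the trial will have one. Entry rests on the MNSI, a leg-and-foot instrument, with no bowel criterion, so the split could be lopsided or few patients might have abnormal stools at all. This stands. A reader might infer that opposite improvements will cancel and that a true benefit will be reported as none. The documents support only that this can happen.

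A second reply is that the recode does not rescue a small trial: with few abnormal patients or a modest response, distance from centre is underpowered too. This also stands, and the case for the recode should not be made on recovered power alone. Its firmer ground is that the result can then be interpreted.

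A third reply is that little depends on this scale. The sample size rests on the TCSS. BEST serves the same objective and runs from 0 (best) to 100 (worst), and its first item asks about disturbed bowel habit in either direction. A reader might infer that the trial's main conclusions, or its whole gastrointestinal objective, are compromised; they are not. However, BEST asks about impact, worry and mood, not stool form, so it does not replace what the Bristol scale was included to measure.

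Finally, type 4 as the centre appears nowhere in the protocol. It is used here only for illustration.

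**Conclusion.** The point holds in a limited form. As planned, a significant Bristol result has no reading as better or worse, and this does not depend on any assumption about the patients. Separately, a real benefit can read as no effect. Under the assumed inputs, raw-score power runs from about 5–6% when the two ends balance to 48% when all abnormal patients are constipated, against 26–91% for distance from type 4 on the same data. Baseline mix, response rate, size of move, noise and centre are all assumptions, so these figures show a range and do not predict this trial.

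It concerns one secondary measure, alongside another gastrointestinal measure that is free of the defect. The change is worth making because it is cheap, but it ranks low among recommended changes.

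**What to change.** In sections 8.6 and 8.8, before unblinded analysis:

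1. The investigators state the normal Bristol type or band.
2. The Bristol analysis becomes the distance from that type or band, compared between arms at month 3 with adjustment for baseline distance.
3. As support, report the share of patients inside the band in each arm.
4. Show raw types only as a frequency table by arm and visit.

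While editing the entry, correct the count of categories: section 8.6 says 6, but the range is 1 to 7 and Appendix 6 lists seven types.

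The cost is wording only: same data, visits and patients. The one small downside is that the centre or band must be fixed in advance. The schedule in section 10 places statistical analysis in January–June 2022 and the document was last updated in March 2025. If arms have already been compared unblinded, the recoded analysis should be labelled post hoc.

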8.7 STRATEGIC PLAN

Through an open invitation, subjects living with T2D who meet the inclusion criteria will be invited to be assessed and tested at Anáhuac México Norte University, the Kidney Specialty Center, and the Nueva Oxtotitlán Clinic (Toluca), as appropriate. The invitation will be extended, explaining the procedures, duration, and ethical issues; if the subject decides to participate, he or she will be asked to sign the informed consent letter (Annex 1). Once the subject enters the protocol, he or she will be randomized (using a random number table previously generated in a spreadsheet) to the experimental group (diet + capsules with cocoa) or the control group (diet + capsules with methylcellulose).

The study will last three months and patients will be seen on four occasions: at the beginning (baseline measurement), at the first and second month (review appointments) and at the third month (final measurement).

Patients will be asked to attend the appointments on an empty stomach, after having urinated and defecated. Weight will be determined according to the Lohman technique, that is, without shoes and with as few clothes as possible, the individual will be placed in the center of the scale and must remain still during the measurement. (54) Waist circumference will be measured according to the proposal of the Ministry of Health of Mexico: placing the tape in a horizontal plane around the waist, taking as reference the mid-axillary line, locating the midpoint between the lower costal margin and the highest lateral edge of the iliac crest (55) and the abdominal circumference: the upper part of the hip bone and the upper part of the right iliac crest are located and the measuring tape is placed in a horizontal plane around the abdomen, at the level of the iliac crest, at the end of a normal expiration. (55) Likewise, blood pressure will be measured using a sphygmomanometer (Nebucor brand, model HL-888JA), according to the Clinical Practice Guide for the Diagnosis and Treatment of Arterial Hypertension in the first level of care (57). These evaluations will be carried out every month, until completing the three months of the duration of the study. In addition, at the beginning of the study the MNSI (Annex 3) will be applied as part of the diagnosis of DN, and both at the beginning and at the end, the TCSS (Annex 4), the questionnaire as the physical examination (51), the BEST questionnaire (Annex 5), the Bristol scale (Annex 6) and the Diabetes 39 quality of life questionnaire (Annex 7) will be applied and laboratory studies will be taken to know the biochemical parameters (triglyceridemia, HDL-c, LDL-c, glycemia,

HbA1c, TG / HDL index and neutrophil/lymphocyte ratio will be determined, as described in the table of variables.

Participants in both groups, being subjects with a cardiometabolic disease, will be nutritionally assisted, that is, all patients will be given a meal plan according to the characteristics of each one of them, calculated by the Mifflin-St. Jeor energy expenditure prediction formula (67) for subjects with obesity, while, according to the Joslin Diabetes Center, a distribution of 40-45% carbohydrates, 30-40% lipids, and 20-30% protein is suggested. (68) Two capsules will be prescribed – cocoa for the experimental group or methylcellulose for the control group – in the morning and two capsules at night.

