3.2 Feasibility

In order to carry out this research project, work will be carried out at the facilities of the Anáhuac México Norte University, at the Kidney Specialty Center (State of Mexico) and at the Nueva Oxtotitlán clinic (Toluca), where the tests will be carried out with the patients. The equipment to carry out the electrophysiology tests (electrical recording and stimulation) is already available, as well as the cocoa capsule supplement, so the study can be carried out without setbacks. Cocoa supplementation does not affect the patients' dietary regimen or compromise their regular medication. In addition, the RDD of the H reflex test does not produce adverse effects, is painless and noninvasive.

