8. METHODOLOGY

8.1 Study Type: Explanatory

8.2 Design: Double-blind, randomized controlled clinical trial.

8.3 Study population: Adult subjects aged 40-60 years diagnosed with type 2 diabetes mellitus and diabetic neuropathy who attend, by open call, to Anáhuac México Norte University, the Kidney Specialty Center in the State of Mexico, and the Nueva Oxtotitlán clinic (Toluca).

8.4 Sample Size Calculation:

$$N = \frac{2(Z\alpha+Z\beta^2)s^2}{d^2} = N = \frac{2(1.96+0.84^2)(0.84)^2}{(0.776)^2} = N = \frac{(15.68)(0.7056)}{(0.6021)}$$

A total of 18 subjects per group were obtained, considering the following data:

s= Baseline standard deviation: 0.84 (obtained from a study in which probucol and methylcobalamin are used in subjects with DN and the TCSS is used to assess the effect of the intervention.) (49)

d= Proposed difference: 0.776 (refers to the expected difference → 7.5% decrease with respect to the control group)

Z α = 1.96 (value in tables, corresponding to a significance level of 95% for two tails)

Z β = 0.84 (value in tables, corresponding to a power of 80%)

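### No blocking or site stratification is described across three sites, and the between-arm test uses neither site nor baseline, so precision is lost if sites differ.

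*Combined protocol and SAP*

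**What the plan says.** - **Allocation (8.7).** Subjects are randomised to cocoa or methylcellulose capsules "using a random number table previously generated in a spreadsheet". No allocation ratio, block size, stratum, separate list per site or holder of the list is given.
- **Sites (3.2, 8.3, 8.7).** Subjects are assessed at "Anáhuac México Norte University, the Kidney Specialty Center, and the Nueva Oxtotitlán Clinic (Toluca), as appropriate": a university, a kidney specialty centre and a clinic.
- **Sample size (8.4).** "A total of 18 subjects per group were obtained", from "s= Baseline standard deviation: 0.84" and "d= Proposed difference: 0.776" on the Toronto Clinical Scoring System (TCSS), with two-sided 5% significance and 80% power.
- **Outcome (8.6).** The TCSS "is a clinical evaluation system carried out by the researcher". It is scored at the start and at the end (8.7).
- **Between-arm test (8.8).** Student's t-test for "independent samples, or if applicable, with Mann-Whitney U at each measurement time". There is no site term and no use of the baseline value.

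**The concern.** With about 36 subjects over three dissimilar sites, a bare random number list leaves both the arm sizes and the site mix of each arm to chance. If TCSS levels differ between sites, because of the patients or the examiners, a test without a site term puts that difference into the residual error. The design has little room for this: its own formula gives slightly more than 18 per arm, and 8.4 makes no allowance for subjects removed under the elimination criteria in 8.5. The baseline TCSS would absorb part of any stable site difference, but the between-arm test does not use it.

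**Working it through.** **Inputs from the documents:** SD 0.84, difference 0.776, Z values 1.96 and 0.84, 18 per arm (8.4); three sites (8.7); unadjusted test (8.8).

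**Assumptions, not in the documents:** 1:1 simple allocation, 12 subjects per site, one site shifted by Δ points, and normal outcomes. Simulations used 20,000 trials per cell, with a Monte Carlo error of about 0.3 points.

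**1. The plan's own figure.** n = 2(1.96 + 0.84)² × 0.84² / 0.776² = 15.68 × 0.7056 / 0.6022 = 18.37. The plan gives 18; rounding up gives 19. At 18 v 18, power is 79.1% (normal) or 76.8% (t-test).

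**2. Arm sizes alone.** Under Binomial(36, 0.5), P(18:18) = 13% and P(14:22 or worse) = 24%. Normal-theory power is 77.1% at 14:22. Averaged over all splits it is 78.0%, against 79.1% at 18:18, a loss of about 1 point.

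**3. Site mix.** P(a given site of 12 splits 4:8 or worse) = 0.388. P(at least one of three does) = 1 − (1 − 0.388)³ = 77%.

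**4. Error term if 0.84 is a within-site SD.** One site in three shifted by Δ adds variance Δ² × (1/3)(2/3) = 2Δ²/9. Total SD = √(0.84² + 2Δ²/9) = 0.872, 0.963 and 1.098 for Δ = 0.5, 1 and 1.5.

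**5. Simulated power, no baseline term.**

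| Δ | Simple list, no site term (as written) | Simple list + site term | Site blocks + site term |
|---|---|---|---|
| 0 | 76% | 73% | 76% |
| 0.5 | 72% | 73% | 77% |
| 1 | 64% | 73% | 77% |
| 1.5 | 52% | 73% | 77% |

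Type I error of the test as written stays at 0.049 to 0.052. Site blocks without a site term make the t-test conservative: type I error is 0.042, 0.024 and 0.010 at Δ = 0.5, 1 and 1.5. A different pattern, with sites at −g, 0 and +g, gives the same picture: 66% at g = 0.5 and 47% at g = 1 as written, against about 76% with blocks and a site term.

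**6. If 0.84 is a total SD.** The within-site SD is √(0.84² − 2Δ²/9) = 0.806 at Δ = 0.5 and 0.695 at Δ = 1. Power as written stays at 75 to 76%. Site blocks plus a site term give about 80 to 81% and 90%.

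**7. Adding baseline (within-site SD 0.84).** The baseline-to-final correlation ρ is not in the documents, so a range is shown.

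| ρ within site | Simple list, arm + baseline, Δ = 0 / 1 | Simple list, arm + baseline + site, Δ = 0 / 1 |
|---|---|---|
| 0.3 | 78% / 73% | 75% / 75% |
| 0.5 | 85% / 83% | 83% / 83% |
| 0.7 | 96% / 95% | 94% / 94% |

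At ρ = 0.5 and Δ = 1, baseline alone lifts power from 64% to 83% with the list unchanged.

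**The case against.** **The size rests on unsupported inputs.** No document gives a between-site difference or site sizes. A 1-point shift is 1 / 0.84 = 1.2 planning SDs and exceeds the planned effect of 0.776. Section 8.4 calls 0.84 only a baseline SD from a cited study; if it already includes site variation, nothing falls below plan. This stands, so the power figures are illustrative.

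**Stronger readings that the documents do not support:**
- A reader might infer that the list is known to be unrestricted. That is the natural reading of a bare random number table, but a list made in advance could have been balanced. What is shown is that no restriction is described.
- A reader might infer false positives or bias. Under simple allocation the type I error stays near 5%, and chance site imbalance is already covered by the t-test's standard error.
- A reader might take unequal arms as the main harm. They cost about 1 point of power, and blocking could not guarantee 18:18 analysed, because 8.5 removes subjects after allocation.
- A reader might infer different examiners at each site. Section 8.6 says only that the researcher scores the TCSS. The H-reflex adds little here: 8.7.1 sets the stimulus for each subject and uses a within-subject amplitude ratio.

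**Blocking may no longer be possible.** Section 10 schedules recruitment for 2021, and the document was last updated in March 2025. If allocation is complete, only the analysis can change. A site term alone then costs about 3 points if sites do not differ (73% v 76%), gains almost nothing at Δ = 0.5, and does not reach 77%. This stands, and it moves the weight of the remedy to baseline adjustment.

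**Conclusion.** The point holds as a loss of precision, conditional on sites differing. The plan describes no restriction on allocation across three sites and specifies an unadjusted comparison that ignores both site and an available baseline. If 0.84 is a within-site SD, the illustrative loss against site blocks plus a site term is about 5, 13 and 25 points of power at shifts of 0.5, 1 and 1.5. If 0.84 is a total SD, the plan keeps about 75% and forgoes a gain of about 5 to 15 points at shifts of 0.5 and 1. If sites do not differ, site blocks with a site term cost essentially nothing. The case for using baseline does not need a site difference, but its gain depends on the correlation: with the existing list and a site term, power is 75%, 83% and 94% at ρ = 0.3, 0.5 and 0.7. A change is advisable. It does not bear on the validity of the test.

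**What to change.** **In 8.8, whatever the state of allocation:** make the between-arm comparison of final TCSS, and of the other outcomes measured at baseline and at the end, a linear model with arm, baseline value and site. If normality fails, use a rank-based version of the same model in place of Mann-Whitney. Fix this in writing before unblinding, and state that it was done blind.

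**In 8.7:** state the allocation ratio, how the list was made, any restriction on it and who held it.

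- *If allocation is not complete:* generate the list as permuted blocks of varying size within each site, held by someone who neither enrols nor assesses. Always pair this with the site term, because stratifying without it makes the t-test conservative.
- *If allocation is complete:* keep the list. Baseline adjustment is then the main gain.

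**Cost:** no extra subjects or visits; an edit to the spreadsheet if it is still in use, and a short addition to 8.8. The model spends two degrees of freedom on site and one on baseline. Under the existing list the site term costs about 3 points of power if sites do not differ. If baseline turned out to be uncorrelated with the final value, including it would cost about 1 point.
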